7.5.4 General Dose Adjustment Note

The severity of DLTs/AEs will be graded according to the NCI CTCAE v5.0. Reasons for dose modifications or delays, the supportive measures taken, and outcome should be documented in patient's chart and recorded in the CRF.

- For any concomitant conditions already apparent at baseline, dose modifications will apply according to corresponding shift in toxicity grade, if investigator feels it is appropriate. For example, if a patient has Grade 1 asthenia at baseline that increases to Grade 2 during treatment, this will be considered a shift of 1 grade and treated as Grade 1 toxicity for dose-modification purposes.
- For toxicities that are considered by investigators to be unlikely to develop into serious or life-threatening events, treatment can be continued at the same dose.
- To recover from acute toxicity, unless otherwise indicated, treatment can be delayed for up to 14 days. If a treatment delay is required for 14 days or longer, treatment should be discontinued. Continuation/resumption of treatment after an interruption of 14 days or more must be discussed with the sponsor.
- Where several toxicities with different grades or severity occur at the same time, dose modifications should be according to highest grade observed.

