6.2 Discontinuation or Withdrawal

6.2.1 Discontinuation of Treatment

6.2.1.1 Permanent Discontinuation of Treatment

The investigator has the right to discontinue a patient from the study for any medical condition that the investigator or sponsor determines is in the best interest of the patient; reasons may include non-compliance (eg, missed doses, visits) or pregnancy.

Any patient who discontinues treatment should be encouraged to return to the study site for an EOT Visit and continue with the remaining study visits. The primary reason(s) for discontinuation must be recorded on appropriate CRF.

Patients must be discontinued from treatment for disease progression, withdrawal of consent, intolerable toxicity, as outlined in [Table 8](#), [Table 9](#), and [Table 10](#), repeated non-compliance or poor compliance, commencement of other antitumor treatment during the study, pregnancy, loss to follow-up, termination of the study by the sponsor, death, or end of the study.

Patients may receive a maximum of 6 cycles of therapy unless the following are met:

- Patients with AML must have a partial response (PR) or better based on the 2017 ELN criteria ([Appendix 8](#)).
- Patients with HR-MDS must have a hematological response or better based on the IWG Criteria ([Appendix 12](#))
- Patients with AITL must have a stable disease (SD) or better based on the Lugano Classification ([Appendix 9](#)).

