6.2.2 Study Stopping Rules

Safety will be monitored continuously throughout the conduct of the study by a standing SRC. There will be periodic review of emerging data on safety, PK, drug exposure, TE, PD, and clinical response to determine continuation (or otherwise) of individual patient, cohorts, arms, or entire dose expansion part. If the study is halted as per Study Stopping Rules (Section 6.2.2.2) in either the dose escalation part or the dose expansion part, the study will only be restarted after Regulatory Approval as per local regulations.

Dose stopping rules for individual patients common to both dose escalation and dose expansion parts include:

1. DLTs that occur outside the DLT assessment window (DLT-equivalent) that have not resolved to Grade 1 or lower within 14 days, or after medical intervention as specified in Section 4.1.1.
2. Progression of disease that leads to treatment discontinuation
3. In the opinion and recommendation of the PI, or individual patient on their own, may withdraw from study at any time
4. If there is documented evidence of repeated non-compliance

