7.5 Dose Adjustments

7.5.1 Adjustment of Dose Within the DLT Assessment Window

In the DLT assessment window, patients without DLT must not undergo dose reduction of HMPL-306.

- If a DLT occurs, HMPL-306 administration will be suspended and appropriate supportive treatment will be given.
- If a DLT returns to Grade 1 (inclusive) or lower within 14 days, HMPL-306 may be resumed at the previous lower dose if the investigator assesses that the patient may still benefit.
- If a DLT has not returned to Grade 1 (inclusive) or lower within 14 days, or DLT reoccurs at the lowered dose, HMPL-306 treatment will be terminated.
- If a patient experiences a Grade 4 nonhematologic toxicity, HMPL-306 treatment will be terminated.

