7.5.2 Dose Adjustment Outside the DLT Assessment Window (Including Dose Expansion Part)

Dose adjustments are to be made for any AE deemed at least possibly related to HMPL-306.

Dose adjustments are to be made as outlined in [Table 8](#) and [Table 9](#).

Table 8 Dose Adjustment for Hematologic Toxicity

CTCAE v5.0 Grade	Action
Grade 1 or 2	None
Grade 3 or 4 (believed to be related to HMPL-306 and NOT underlying disease)	
Hold drug.If the toxicity improves to Grade ≤ 2 within 7 days, then resume at original dose.If the toxicity recurs at original dose, then resume 1 dose level lower provided the toxicity improves to Grade ≤ 2 within 7 days.If the toxicity recurs in setting of prior dose level reduction, then resume 1 additional dose level lower provided the toxicity improves to Grade ≤ 2 within 7 days.In the event the toxicity does not improve to Grade ≤ 2 within 7 days or toxicity recurs despite 2 dose reductions, HMPL-306 treatment is to be permanently discontinued.

CTCAE=Common Terminology Criteria for Adverse Events.

Table 9 Dose Adjustment for Nonhematologic Toxicity

CTCAE v5.0 Grade	Action
Grade 1 or 2	None
Grade 3	
Hold drug.If the toxicity improves to Grade ≤ 2 within 7 days, then resume at original dose.If the toxicity recurs at original dose, then resume 1 dose level lower provided the toxicity improves to Grade ≤ 2 within 7 days.If the toxicity recurs in setting of prior dose level reduction, then resume 1 additional dose level lower provided the toxicity improves to Grade ≤ 2 within 7 days.In the event the toxicity does not improve to Grade ≤ 2 within 7 days or toxicity recurs despite 2 dose reductions, HMPL-306 treatment is to be permanently discontinued.
Grade 4	Permanently discontinue treatment with HMPL-306.

CTCAE=Common Terminology Criteria for Adverse Events.

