8.1.3 Dose-Limiting Toxicity

DLT is defined as occurrence of any of the following TEAEs during the DLT assessment window, unless clearly unrelated to the study drug as per investigator’s discretion:

- Nonhematologic toxicity:
 - TEAEs of Grade ≥ 4
 - Grade ≥ 3 with the exception of those that resolve within 72 hours of onset
- Hematologic toxicity, with the exception of neutropenia or thrombocytopenia that occurs with active leukemic disease:

- Grade 3 or 4 neutropenia lasting more than 7 days
- Grade 4 thrombocytopenia or Grade 3 thrombocytopenia with bleeding or any requirement for platelets transfusion
- Grade 3 or greater febrile neutropenia defined as absolute neutrophil count $1000/\text{mm}^3$ with a single temperature of $>38.3^\circ\text{C}$ (101°F) or a sustained temperature of $\geq 38^\circ\text{C}$ (100.4°F) for more than 1 hour
- Any TEAE requiring a dose delay of ≥ 14 days
- Cases of confirmed Hy's law

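### Outside the DLT window, the protocol does not make clear that Table 9's permanent stop for Grade 4 nonhematologic toxicity prevails over the baseline-shift rule (7.5.4) or the dose-expansion resumption rule (6.2.2.1)

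*Protocol*

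**What the plan says.** Five parts of the protocol bear on a related Grade 4 nonhematologic event.

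- **Section 7.5.2, Table 9** (outside the DLT window, including expansion). The Grade 4 row reads "Permanently discontinue treatment with HMPL-306". The Grade 3 row is a hold, with return to the original dose if the event reaches Grade 2 or lower within 7 days. Grades 1 and 2 need no action.
- **Section 7.5.4.** For concomitant "conditions already apparent at baseline, dose modifications will apply according to corresponding shift in toxicity grade, if investigator feels it is appropriate". The worked example takes asthenia from Grade 1 at baseline to Grade 2 on treatment and says "this will be considered a shift of 1 grade and treated as Grade 1 toxicity for dose-modification purposes". No bullet excepts Grade 4.
- **Section 6.2.1.1.** "Patients must be discontinued from treatment for disease progression, withdrawal of consent, intolerable toxicity, as outlined in" Tables 8, 9 and 10. It does not say whether the observed or the shifted grade is meant.
- **Section 6.2.2.** An individual patient stops for "DLTs that occur outside the DLT assessment window (DLT-equivalent) that have not resolved to Grade 1 or lower within 14 days". Under Section 8.1.3, nonhematologic "TEAEs of Grade" 4 or higher are DLTs, so the same event outside the window is DLT-equivalent.
- **Section 6.2.2.1, Dose Expansion, items 2 and 3.** Resolution of a DLT-equivalent event decides between interruption, reduction and discontinuation. It also decides whether the patient resumes, at the investigator's discretion, with the same dose level among the options.

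Inside the DLT window there is no ambiguity. Section 7.5.1 says: "If a patient experiences a Grade 4 nonhematologic toxicity, HMPL-306 treatment will be terminated".

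**The concern.** The Grade 4 stop is the firmest toxicity rule the protocol has outside the DLT window. It looks deliberate: the history of Amendment 1 (Appendix 18) attributes both the removal of restart after Grade 4 events in 7.5.1 and the dose-adjustment tables in 7.5.2 to a regulator's request. Yet a general note placed after the tables, and a separate stopping section, can each be read as allowing dosing to continue or resume after such an event.

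What is at stake is individual patient safety and consistency between sites. Two investigators could handle the same Grade 4 event differently and both cite the protocol. Section 8.4, the fallback scale for events not listed in CTCAE, describes Grade 4 as life-threatening. Life-threatening events are SAEs reportable within 24 hours, and the Safety Review Committee monitors benefit-risk in expansion, but neither compels a stop. No estimand, sample size or analysis depends on the answer.

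**Working it through.** This is a check of rules rather than a statistical calculation. It assumes a nonhematologic event at least possibly related to HMPL-306, outside the DLT window, not QTcF prolongation (Table 10 uses absolute milliseconds) and not handled under Section 7.6. Recovery thresholds in Table 9 and 6.2.2 are taken as absolute grades.

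**Step 1: reproduce the protocol's example.** Shift = on-treatment grade − baseline grade = 2 − 1 = 1, handled as Grade 1. This agrees with 7.5.4.

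**Step 2: apply the same rule to an observed Grade 4.** Let b be the baseline grade. The shift is 4 − b. The last column is b − 1, the number of grades below baseline the event must fall to reach Grade 1 and so escape the 14-day stop in 6.2.2.

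| b | Shift (4 − b) | Table 9 row reached | Grades better than baseline needed for 6.2.2 (b − 1) |
|---|---|---|---|
| 1 | 3 | Grade 3: hold; original dose if Grade ≤2 within 7 days, otherwise permanent stop | 0 |
| 2 | 2 | No action | 1 |
| 3 | 1 | No action | 2 |

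With the shift, the permanent-stop row is reached in 0 of 3 cases; without it, in 3 of 3. For b = 1, a return to baseline satisfies 6.2.2, so the permanent stop can be avoided. For b = 2 or 3, the patient would have to become better than at baseline within 14 days, so the stop would usually come late rather than not at all.

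**Step 3: doses in the interval.** For b = 1 the drug is held: 0 doses during the hold. For b = 2 or 3 in Part 1, the theoretical maximum is 14 days × 1 dose per day = 14, against 0 under Table 9. That assumes uninterrupted dosing and no resolution before day 14. No such figure is given for Part 2, because 6.2.2.1 speaks of resuming, which presupposes interruption.

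**Step 4: does *dose modifications* in 7.5.4 cover discontinuation?** Usage is mixed.

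- *Against:* protocol 8.6.4 and 9.2.4 list modification and discontinuation separately, and SAP 4.3 limits dose modifications to interruption and reduction.
- *For:* Table 9 is headed as a dose adjustment and lists permanent discontinuation among its actions, 7.5.4 itself deals with discontinuation after long delays, and SAP 4.4.2 counts withdrawal as a study drug modification.

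**Step 5: the second path.** Section 6.2.2.1 does not depend on baseline grade or on 7.5.4. A Grade 4 nonhematologic event in Part 2 is DLT-equivalent, and once it resolves, items 2 and 3 allow resumption at the same dose. Table 9 forbids this, and neither section refers to the other.

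**The case against.** The strongest reply is that Table 9 already prevails. Section 6.2.1.1 is worded as an obligation, while 7.5.4 is a discretionary general note whose only example is a Grade 1 to Grade 2 change. On the narrower meaning of *dose modifications*, the permanent stop lies outside the shift rule altogether. This reply stands in part. It is why a reader who infers that 7.5.4 definitely removes the immediate stop at every baseline grade goes too far: the documents support an unstated hierarchy, not an override. But the obligation in 6.2.1.1 refers back to the tables without saying which grade enters them, so it does not settle the matter.

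A second reply is that the situation will be uncommon. Toxicity from prior cancer therapy must have recovered to below Grade 1, ECOG status must be 0 to 2, bilirubin and creatinine clearance are bounded, and exclusion 17 removes patients at high risk of treatment complications. This also stands. Baseline Grade 3 nonhematologic conditions should be unusual, and the 3 cases in the table are combinations of grades, not patients. The path is not closed, though: inclusion criterion 5 waives the AST/ALT limit when the elevation is attributed to leukemia and states no upper bound for that waiver.

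A third reply concerns the other 7.5.4 bullet, under which "treatment can be continued at the same dose". It is confined to toxicities judged unlikely to become serious or life-threatening, so it should not reach Grade 4 and adds little to the problem.

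**Conclusion.** The point holds as a gap in clarity. Outside the DLT window the protocol does not establish that Table 9's permanent stop for Grade 4 nonhematologic toxicity takes precedence. Two texts permit another course: the baseline-shift rule in 7.5.4, if dose modifications include discontinuation, and the Part 2 resumption rule in 6.2.2.1, at any baseline grade. Both are permitted, neither is mandated, and 6.2.2 remains a real 14-day backstop.

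A reader might also infer that Part 2 patients could take up to 14 further doses through an ongoing Grade 4 event. Section 6.2.2.1 does not support that. The 14-dose figure is only a theoretical maximum for Part 1 at baseline Grade 2 or 3.

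The documents give no frequency and none is claimed. Reach is small: the SAP (5.1.1, Table 13 footnote) reports a single Part 2 patient at the expansion dose, and in Part 1 the question arises only outside the 28-day DLT window. Confidence is moderate, because the 7.5.4 path depends on a contestable reading. This is a cheap improvement worth making for patients still on treatment or for any later protocol that reuses this text.

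**What to change.** Add to Section 7.5.4:

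> The baseline-shift rule does not apply to an observed CTCAE Grade 4 nonhematologic toxicity at least possibly related to HMPL-306; Table 9 governs (Section 7.5.1 within the DLT assessment window), except as specified in Section 7.6.

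Add to Section 6.2.2.1, Dose Expansion, items 2 and 3:

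> Resumption does not apply to Grade 4 nonhematologic toxicity, for which Table 9 requires permanent discontinuation, except as specified in Section 7.6.

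Both are needed: amending 7.5.4 alone would leave the Part 2 resumption path open. The Section 7.6 exception keeps the differentiation syndrome pathway, which allows resumption after improvement. Naming the second 7.5.4 bullet is optional. Whether the shift rule may soften the Grade 3 hold is a clinical choice and is left alone.

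The cost is two sentences and a memo to sites, with no new data. The downside is less investigator discretion, for example for an asymptomatic Grade 4 laboratory value in a patient whose baseline was already abnormal. Table 9 already denies that discretion when the shift is not used.

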7.6 Special Adverse Events Handling Principles

7.6.1 Differentiation Syndrome Handling Principles

Patients receiving HMPL-306 treatment are at risk of developing DS. According to relevant literature ([Montesinos 2009](#)), it is recommended that for patients with ≥ 2 items of the following

HUTCHMED Limited

Page 71

8 clinical symptoms, when related symptoms cannot be explained by other reasonable reasons, they should be diagnosed with DS and furthermore, in addition to grading as based on the NCI CTCAE v5.0, DS Montesinos grading also needs to be performed as per [Table 11](#). The 8 clinical symptoms include unexplained fever, dyspnea, weight gain (>5 kg), unexplained hypotension, acute renal failure, interstitial lung infiltration, pleural effusion, or pericardial effusion. Symptoms, laboratory tests, or abnormal vital signs for each AE by name may be referred to in [Table 11](#). Patients who do not meet aforementioned criteria but are assessed by the investigator to have suspected DS should also be reported as having DS (Section [8.1.4](#)). For patients who have or are suspected of having developed DS, the investigator must report AEs as per the requirements in Section [8.2](#), for which patients should be closely monitored, and treated using following measures in a timely manner:

- Dexamethasone 10 mg and hemodynamic monitoring every 12 hours are immediately administered for at least 3 days or until symptoms disappear.
- Interrupt HMPL-306 if severe pulmonary symptoms requiring intubation or ventilator support and/or renal dysfunction persist for more than 48 hours after initiation of dexamethasone.
- Based on peripheral WBC count, hydroxyurea up to 2000 to 3000 mg twice daily (BID) is given orally for treatment.
- If clinically necessary, patient is given furosemide for treatment.
- Leukapheresis is performed if clinically necessary.

When the above treatment measures are unable to effectively control clinical features of DS, HMPL-306 treatment should be suspended. HMPL-306 administration can resume when signs and symptoms improve to Grade 2 or lower at a dose that should be decided after discussion with the sponsor.

Table 11 Differentiation Syndrome Diagnosis and Montesinos Grading Criteria

Diagnosis	Montesinos Grading	
	Moderate	Severe
Differentiation syndrome (≥ 2 symptoms)	2-3 symptoms	≥ 4 symptoms
Symptoms: Unexplained fever, dyspnea, weight gain (>5 kg), unexplained hypotension, acute renal failure, interstitial lung infiltration, pleural effusion, or pericardial effusion		

7.6.2 Handling Principles for Noninfectious Leukocytosis

Noninfectious leukocytosis is defined as WBC $>25 \times 10^9/L$ or an absolute increase in total WBC of $>15 \times 10^9/L$ from baseline. Patients should be treated using following measures in a timely manner:

- Hydroxyurea oral therapy per institutional standards
- Leukapheresis is performed if clinically necessary

When above treatment measures are unable to effectively control the clinical symptoms, HMPL-306 treatment should be suspended. Prior to resuming study drug WBC should be $<30 \times 10^9/L$ in addition to resolution of clinical features of DS. After clinical features have been fully relieved, HMPL-306 administration can resume at a dose that should be decided after discussion with the sponsor.

8 SAFETY MONITORING

8.1 Definitions

8.1.1 Adverse Event

An AE is any unfavorable and unintended sign, symptom, or disease temporally associated with the use of an investigational medicinal product or other protocol-imposed intervention, whether or not considered related to study drug.

8.1.2 Serious Adverse Event

An AE is considered “serious” if, in the view of either the investigator or sponsor, it results in any of the following outcomes:

- Death.
- A life-threatening AE. An event is considered “life-threatening” if, in the view of the investigator, its occurrence places the patient at immediate risk of death. It does not include an AE or suspected adverse reaction that, had it occurred in a more severe form, might have caused death.
- Inpatient hospitalization or prolongation of existing hospitalization.
- A persistent or significant incapacity or substantial disruption of the ability to conduct normal life functions.
- An abnormal pregnancy outcome (eg, spontaneous abortion, fetal death, stillbirth, congenital anomaly, birth defect, or ectopic pregnancy) in a child born to a female patient or female partner of a male patient exposed to study drug.
- Important medical events that may not result in death, be life-threatening, or require hospitalization may be considered serious when, based upon appropriate medical judgment, they may jeopardize the patient and may require medical or surgical intervention to prevent one of the outcomes listed in this definition. Examples of such medical events include allergic bronchospasm requiring intensive treatment in an emergency room or at home, blood dyscrasias or convulsions that do not result in inpatient hospitalization, or the development of drug dependency or drug abuse.

8.1.3 Dose-Limiting Toxicity

DLT is defined as occurrence of any of the following TEAEs during the DLT assessment window, unless clearly unrelated to the study drug as per investigator’s discretion:

- Nonhematologic toxicity:
 - TEAEs of Grade ≥ 4
 - Grade ≥ 3 with the exception of those that resolve within 72 hours of onset
- Hematologic toxicity, with the exception of neutropenia or thrombocytopenia that occurs with active leukemic disease:

- Grade 3 or 4 neutropenia lasting more than 7 days
- Grade 4 thrombocytopenia or Grade 3 thrombocytopenia with bleeding or any requirement for platelets transfusion
- Grade 3 or greater febrile neutropenia defined as absolute neutrophil count $1000/\text{mm}^3$ with a single temperature of $>38.3^\circ\text{C}$ (101°F) or a sustained temperature of $\geq 38^\circ\text{C}$ (100.4°F) for more than 1 hour
- Any TEAE requiring a dose delay of ≥ 14 days
- Cases of confirmed Hy's law

8.2 Adverse Event Reporting

8.2.1 Adverse Event Reporting Period

After informed consent, but prior to initiation of study drug, all AEs and SAEs regardless of attribution will be collected. After initiation of study drug, all SAEs and AEs regardless of attribution will be collected until 30 days after the end of treatment or start of a new antitumor therapy, whichever is earlier. After this 30-day period, and if the patient has not started any other antitumor treatment, then investigators should report only SAEs that are considered to be related to the study drug until study discontinuation.

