6.1.13 Safety Evaluation

AEs emerging as a result of protocol-required procedure(s) are collected, even during pre-screening period if applicable. AEs are collected from the signing of the ICF until 30 days after the end of treatment or initiation of new antitumor therapy. Related AEs will be followed

until they are recovered to the baseline status, already in a stable state as assessed by the investigator, start of new antitumor therapy, lost to follow-up, death, withdrawal of informed consent, end of study, or it has been confirmed the AEs are unrelated to the study drug.

Serious adverse events (SAEs) are collected from the signing of the ICF (pre-screening ICF if applicable) until 30 days after the end of treatment or initiation of new antitumor therapy, whichever is earlier. After this 30-day period, and if the patient has not started any other antitumor treatment, investigators should report only SAEs considered to be related to the study drug.

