8.6.8 Death

All deaths that occur during protocol-specified AE reporting period must have their primary underlying cause reported to sponsor as an SAE with death listed as outcome. Deaths due to progression of disease must also be reported to the sponsor as an SAE. If primary cause of death is unknown at the time of reporting and/or if the death was unwitnessed, please record “death of unknown cause,” or “unwitnessed death” in the eCRF and on the SAE report form. The eCRF and SAE report form should be updated when the cause of death has been determined. Death events that occur after 30 days following the end of treatment must be reported to the sponsor as an SAE only if it is confirmed as related to study drug.

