4.4.2. Adverse Events (AEs)

All AEs will be coded from verbatim text to preferred term (PTs) and grouped by system organ class (SOC) using the Medical Dictionary for Regulatory Activities (MedDRA) version 27.1 or higher. AEs will be collected from the time of signature of informed consent throughout the treatment period. AEs will be graded by investigator according to National Cancer Institute (NCI) Common Terminology Criteria for Adverse Events (CTCAE) v5.0. Missing severity grade will not be imputed, and will be summarized as 'Missing Grade' category in the by-grade analysis.

An AE is considered a TEAE:

(i) If one of the criteria is met:

- 1) If the onset date is on or after the start of study treatment until 30 days after the last dose or prior to the start of a subsequent anti-tumor therapy (whichever comes first), or if the onset date is missing; or
- 2) If the AE has an onset date before the start of study treatment, but worsened in severity after the study drug administration (i.e. SAE start date is on or after the start of study

treatment until 30 days after the last dose or prior to the start of a subsequent anti-tumor therapy (whichever comes first);

(ii) Beyond 30 days after the last dose or after the start of a subsequent anti-tumor therapy (whichever comes first), treatment-related SAEs will also be considered as TEAEs.

Investigator assessed AEs causality to study drug will be classified as "Related" and "Not Related". An AE with a missing causality will be classified as "Related" to study drug.

Other AE variables include treatment-related AEs, AEs of special interest (AESI), COVID-19 related AEs, AEs leading to study drug modifications (i.e. dose interruption, dose reduction, or study drug withdrawal), AEs leading to death, and SAEs. The AESI information will be identified programmatically by SMQ/PT.

For AEs which are not on-going, duration of AE (days) is defined as AE end date – AE start date +1; for on-going AEs, the end date will be listed as 'Ongoing'.

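### The SAP counts drug-related SAEs after a switch to new antitumor therapy as TEAEs, but the protocol's reporting-period sections do not ask sites for them

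*Protocol*

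**What the plan says.** The main collection window is in protocol 8.2.1: "all SAEs and AEs regardless of attribution will be collected until 30 days after the end of treatment or start of a new antitumor therapy". The sooner of the two applies. For the time after that, 8.2.1 adds a conditional request, limited to drug-related events and running up to study discontinuation: "After this 30-day period, and if the patient has not started any other antitumor treatment, then investigators should report only SAEs that are considered". Section 6.1.13 carries the same condition: "if the patient has not started any other antitumor treatment, investigators should report only SAEs considered to be related to the study drug".

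Deaths have their own sentence in 8.6.8, which makes a confirmed relation to study drug the test for late deaths: "Death events that occur after 30 days following the end of treatment must be reported to the sponsor as an SAE only if it is". That section does not mention new therapy.

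Two protocol sections ask for SAEs with no end date: 8.2.2 (to the sponsor within 24 hours of awareness, whatever the attribution) and 10.2.

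On the analysis side, SAP 4.4.2(ii) extends the TEAE definition to late related SAEs: "Beyond 30 days after the last dose or after the start of a subsequent anti-tumor therapy (whichever comes first), treatment-related SAEs will also be considered". The same SAP section says AEs are collected through the treatment period. SAP 4.1.4 ends that period before subsequent anti-tumor therapy and restricts safety summaries to it, unless otherwise specified. Protocol 9.2.4 has a different TEAE definition: up to 30 days after end of treatment, with no cut at new therapy and no extension for late related SAEs. SAP Section 7, which lists changes from the protocol, does not mention the TEAE definition.

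**The concern.** SAEs are part of the primary endpoint in both parts. Rule (ii) exists so that a serious event attributed to HMPL-306 is counted even when it arises late or after another drug has been started. It works only if sites are asked for such events.

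Read together, the two sentences of 8.2.1 close the main window at a switch and reopen it for related SAEs only in patients who have not switched. For a patient who has switched, neither 8.2.1 nor 6.1.13 asks for a new SAE, even one the investigator attributes to HMPL-306 and even inside the 30 days. The patients concerned are foreseeable: those who stop for progression or toxicity and move to another therapy. They may also include responders who leave HMPL-306 for transplant, since 6.1.4 groups HSCT with new antitumor regimens and 6.2.1.2 keeps these patients in the study.

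At stake are the completeness of the related-SAE count and the reliability with which these events reach the sponsor and the Safety Review Committee.

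**Working it through.** The point rests on comparing texts, not on a figure in the plan.

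**1. What is requested and what is counted, for a new SAE judged related to HMPL-306**

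| Situation | Requested by 8.2.1 / 6.1.13? | Other protocol text | Counted by SAP 4.4.2(ii)? |
|---|---|---|---|
| No new therapy, beyond 30 days | Yes | – | Yes |
| After a switch, non-fatal | No | 8.2.2 and 10.2, no end date | Yes |
| After a switch, fatal, within 30 days of end of treatment | No | 8.2.2 and 10.2; 8.6.8 ties earlier deaths to the reporting period, which closed at the switch | Yes |
| After a switch, fatal, beyond 30 days | No | 8.6.8 requires it, with no exception for new therapy | Yes |

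The first row is consistent. The second and third rows are the gap. In the fourth row 8.6.8 supplies what 8.2.1 omits, so the two sections need to agree.

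**2. TEAE definitions side by side**

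- Protocol 9.2.4: up to 30 days after end of treatment; no cut at new therapy; no late extension.
- SAP 4.4.2(i): up to 30 days after last dose, cut at subsequent therapy.
- SAP 4.4.2(ii): adds related SAEs beyond either limit.
- SAP 4.1.4 and the collection sentence in 4.4.2: the period ends at subsequent therapy. The proviso in 4.1.4 allows (ii) to stand as an exception for summaries, but the collection sentence still describes no source for the events.

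**3. Direction of the effect**

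The only safety-detection figure in the plan is the chance of at least one AE in 10 expansion patients (protocol 9.1.2.2). It reproduces:

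- 1 − 0.90^10 = 0.651 (stated 65%)
- 1 − 0.95^10 = 0.401 (stated 40%)
- 1 − 0.99^10 = 0.096 (stated 9.6%)

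Suppose a share f of events of a given type goes unrecorded because onset follows a switch. The documents give no value for f; 0 to 50% is an assumption for illustration. The chance of recording at least one event is 1 − (1 − p(1 − f))^10:

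| True rate p | f = 0 | f = 10% | f = 25% | f = 50% |
|---|---|---|---|---|
| 10% | 65.1% | 61.1% | 54.1% | 40.1% |
| 5% | 40.1% | 36.9% | 31.8% | 22.4% |
| 1% | 9.6% | 8.6% | 7.3% | 4.9% |

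This shows direction only. It is not a forecast for this trial: f is unknown, and SAP Table 13 notes that only one patient was enrolled in the expansion cohort.

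**The case against.** The strongest reply is that ending collection at a new anticancer drug is a reasoned choice, because attribution is confounded from then on. That stands for unrelated events, and the stop should remain for them. It does not dispose of the point. The SAP itself counts SAEs that an investigator still judges related after a switch, so the plan has not adopted that choice consistently. Some related attributions will nevertheless be made while the patient is on another drug and will be less certain.

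A reader might infer that no related SAE after a switch is reportable and that the sponsor would never hear of one. The documents do not support that. Sections 8.2.2 and 10.2 ask for SAEs without an end date. Section 11.1.1 has the sponsor review any death whatever its cause, survival follow-up in 6.1.19 continues to death, and SAP 5.2.11.3 tabulates follow-up deaths by primary cause. Some sites may therefore report, and fatal events surface by other routes. What remains is that the section defining the reporting period points the other way, so practice may differ between sites.

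A reader might also take 8.6.8 as assuming that late related SAEs in general are still reported. It covers only related deaths beyond 30 days and is merely silent on new therapy.

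It can also be argued that rule (ii) is the outlier, since the rest of the SAP closes the period at subsequent therapy. The documents do not settle which text was intended. They do show that the texts cannot all be applied as written.

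Finally, reach is limited. With one expansion patient, the issue lies mostly in Part 1, and the SAP already rests on a CRF version of September 2024, so a protocol change may recover little.

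**Conclusion.** The mismatch is real and lies in the current text. SAP 4.4.2(ii) counts related SAEs after subsequent therapy, while protocol 8.2.1 and 6.1.13 request late related SAEs only from patients who have not started one. The consequence is uneven capture between sites and a related-SAE count that can only be too low. It mainly affects non-fatal related SAEs, plus related deaths within 30 days of end of treatment but after a switch. Patients who start no new therapy are unaffected.

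The size cannot be computed: the documents give neither how many patients switched, nor when, nor how many related SAEs followed. It is tempting to express the loss as the share of the 30-day window cut off by an assumed switch date. That would measure calendar days of all-attribution collection, not related SAEs, and the documents give no switch dates.

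The conclusion assumes that sites take 8.2.1 as governing the reporting period. Where they follow 8.2.2 literally, the loss is smaller.

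**What to change.** - **Protocol 8.2.1 and 6.1.13:** state that SAEs considered related to HMPL-306 are reported until end of study whether or not new antitumor therapy has started. Keep the new-therapy stop for unrelated AEs and SAEs.
- **Protocol 8.6.8:** state the same rule for related deaths, so that those within 30 days but after a switch are covered.
- **Protocol 9.2.4, SAP 4.1.4 and SAP 4.4.2:** align the TEAE definition and the treatment-period and collection wording with rule (ii).
- **SAP Section 7:** list the TEAE definition as a change from the protocol.
- **If the data were not collected:** say in the SAP and CSR that rule (ii) is incomplete after subsequent therapy, so that the related-SAE count is not read as complete.

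The cost is wording in both documents and a few extra SAE reports, with no new visits or procedures. The related-SAE count may rise slightly, and some of the added attributions will have been made while the patient was on another drug.
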